4 OBJECTIVES

4.1 Study Objectives

Primary Objectives

The primary objectives of this study are:

- To evaluate safety and reactogenicity of MTBVAC at escalating dose levels compared to BCG vaccine in healthy, BCG naïve, HIV unexposed, South African newborns.
- To evaluate the immunogenicity of MTBVAC at escalating dose levels compared to BCG vaccine in healthy, BCG naïve, HIV unexposed, South African newborns.

Secondary Objective

The secondary objective of this study is:

 To evaluate QFT conversion rates in neonates receiving escalating dose levels of MTBVAC.

Future Exploratory Objective

Samples will be kept for future analyses:

- To evaluate exploratory immune responses to escalating dose levels of MTBVAC and to BCG (including, but not necessarily limited to, analysis of innate response cytokines, specific IgG antibody responses, donor-unrestricted T-cell responses).
- To differentiate vaccine-induced immune responses from natural Mtb infection

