4.2 Study Outcome Measures

4.2.1 Primary Outcome Measures

The primary outcome measures are:

Safety and reactogenicity endpoints:

- Solicited systemic adverse events: fever, irritability, vomiting, diarrhea, drowsiness, poor feeding, skin rash.
- Solicited injection site reaction adverse events: pain, redness, swelling, ulceration, drainage, and regional lymphadenopathy
- Unsolicited adverse events and serious adverse events

Immunogenicity endpoints:

• Frequencies of antigen-specific IFN-γ, TNF-α, IL-2, IL-17 and/or IL-22-expressing CD4 and CD8 T cells measured by 12-hour whole blood (WB) intracellular cytokine staining (ICS) assay at Study Days 28, 56, 182, and 365. Stimulating agents at Study Days 28 and 56 will include MTBVAC, ESAT-6, CFP-10, EspC and a "megapool" of peptides containing immunodominant *M. tuberculosis* epitopes (16). Stimulating agents at Study Days 182 and 365 will include MTBVAC, ESAT-6, CFP-10, EspC and a "megapool" of peptides containing immunodominant *M. tuberculosis* epitopes (16) as well as a modified version of the "megapool" but containing only those epitopes shared by both BCG and MTBVAC.

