10.2.2 Reactogenicity (for Vaccine Studies and Some Therapeutic Trials)

Reactogenicity events are referred to as solicited adverse events. Refer to Section 10.1 for a list of solicited adverse events (systemic and injection site reactions) and timing of collection. Diary cards will be provided to participants for recording of solicited systemic adverse events (for 7 days) and solicited injection site reactions (for 28 days; see Section 9.1 for further details regarding diary cards).

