12.4.4 Safety Analyses

12.4.4.1 Adverse Events

The primary endpoint is the frequency of adverse events (AEs) by MTBVAC dose compared to BCG. In order to assess the primary endpoint, analysis of the data will be preceded by a

blinded data review meeting in order to address population determination and miscellaneous data queries pertinent to analysis of the primary endpoint.

Safety and reactogenicity data will be evaluated by study arm and cohort in all participants in the safety analysis set. The primary variable for evaluation of safety will be the frequency of unsolicited, solicited adverse events and injection site reactions at all available post-vaccination time points. The number and percentage of participants with adverse events will be summarized by MedDRA system organ class (SOC) and preferred term (PT), as well as by severity and relationship to study vaccine. Informal between-group comparisons will be performed using the Chi-square or Fisher Exact test. The Cochran-Mantel-Haenzel test will be used to compare the effect of dose on reactogenicity (injection site adverse events).

Separate listings will be provided for participants with serious adverse events. SAEs may also be summarized by MedDRA system organ class and preferred term.

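### The dose-effect test of reactogenicity covers injection-site events only, although the protocol defines reactogenicity as all solicited events, so no test that uses dose order is planned for the seven solicited systemic events

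*Combined protocol and SAP*

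**What the plan says.** The first primary objective in Section 4.1 is "To evaluate safety and reactogenicity of MTBVAC at escalating dose levels compared to BCG vaccine". Section 10.2.2 fixes the term: "Reactogenicity events are referred to as solicited adverse events", and it points to Section 10.1 for both kinds, systemic and injection-site. Section 4.2.1 lists the systemic kind among the primary outcome measures: "Solicited systemic adverse events: fever, irritability, vomiting, diarrhea, drowsiness, poor feeding, skin rash". It also lists six injection-site events.

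Section 12.4.4.1 sets the analysis. "The primary endpoint is the frequency of adverse events (AEs) by MTBVAC dose compared to BCG". Safety and reactogenicity data are evaluated by study arm and cohort, and adverse events are summarized by severity and by relationship to vaccine. Then: "Informal between-group comparisons will be performed using the Chi-square or Fisher Exact test". One further test is named: "The Cochran-Mantel-Haenzel test will be used to compare the effect of dose on reactogenicity (injection site adverse events"). It gives no form of the statistic, dose scores or strata, and does not say whether BCG infants enter the test.

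Section 12.1 rules out formal hypothesis testing. Section 12.4 leaves detail to a statistical analysis plan to be finalized before database lock. Section 12.3.1 bases Phase III dose selection on all the safety data available when Cohort 3 completes Day 182.

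**The concern.** The analysis section uses a narrower meaning of reactogenicity than the protocol's own definition. Of the 13 solicited events in Section 4.2.1 (seven systemic, six local), the seven systemic ones fall outside the only test described as examining the effect of dose.

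This matters because the trial covers a 100-fold dose range (2.5 x 10^4 to 2.5 x 10^6 CFU), the top dose has no infant safety data yet (Section 3.3.1), and one dose will go forward to Phase III. The pattern to look for is a steady rise in reactions with dose. A comparison that treats the arms as unordered is less sensitive to that pattern than one that uses the order. The pausing rules in Section 10.5 are not built to show a graded rise in mild or moderate fever or poor feeding.

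**Working it through.** **Text check.** Sections 4.2.1 and 10.1 list systemic and local solicited events. Section 10.2.2 calls all of them reactogenicity. The parenthesis in Section 12.4.4.1 keeps only the local ones. No other section names a trend or ordered-dose test for systemic events.

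**Is there a planned figure to reproduce?** No. Section 12.2 gives no effect size, event rate, alpha or power. Only the allocation can be checked: 3 x 25 + 3 x 8 = 99, which agrees.

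**Size of the gap.** Inputs: 25 infants in each of three MTBVAC dose arms (Section 5). Assumed, because the documents do not give them: two-sided 5% level, equally spaced dose scores 1, 2, 3, and the event rates below. Power is by exact enumeration of the three binomial counts.

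- Trend (1-df Cochran-Mantel-Haenszel correlation statistic, one stratum): Q = T²/V, with T = Σ x_i(s_i − s̄) and V = p̄(1 − p̄) Σ n_i(s_i − s̄)² · N/(N − 1). Reject if Q > 3.84.
- Unordered comparison across doses: Pearson chi-square on 2 df. Reject if above 5.99.
- Fisher's exact test, highest against lowest dose, for reference.

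| Rates, low/mid/high dose | Trend | 2-df chi-square | Gain of trend over chi-square | Fisher, high v low |
|---|---|---|---|---|
| 10/20/35% | 59% | 47% | 12 points | 45% |
| 20/35/50% | 63% | 50% | 13 points | 51% |
| 10/20/40% | 73% | 62% | 11 points | 59% |
| 10/10/10% (no effect) | 4.5% | 3.5% | – | 0.9% |

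The trend test gains 11-13 points over the 2-df chi-square. It gains 12-14 points over Fisher, but part of that reflects Fisher's conservatism (0.9% rejection under no effect).

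**Drift between cohorts.** Doses are given in sequential cohorts, so dose and calendar time move together. If background rates were 10/20/30% in Cohorts 1, 2 and 3 (assumed) and dose had no effect, the trend test across the MTBVAC arms would still reject 43% of the time. The 2-df chi-square would reject 32% of the time. The 4.5% null rate holds only without drift.

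**Number of tests.** Any systemic event plus seven individual events, each at any grade and at Grade 2 or higher, makes 8 x 2 = 16 tests. If they were independent at 5%, the chance of at least one false signal would be 1 − 0.95^16 = 56%. The tests are not independent, so this is a rough guide.

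**Fallback design.** If the top dose is not used, there are two MTBVAC doses with 25 + 12 = 37 and 25 + 13 = 38 infants. A trend over two doses is in effect the 2x2 comparison: for 10% v 25% (assumed), power is 40% for the trend statistic and 42% for Pearson chi-square.

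**The case against.** The sponsor can fairly say that systemic events are not neglected. The primary endpoint is event frequency by MTBVAC dose, the arms are the doses, and between-group tests are planned. A reader might infer that no dose analysis exists for systemic events, or that only pairwise tests of about 25 against 24 infants are planned. The text supports neither: events are tabulated and compared by dose arm, and the phrase about between-group comparisons admits one chi-square across all arms. Only the use of dose order is missing.

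A reader might also infer that local events get a trend test which systemic events are denied. Section 12.4.4.1 does not say so. The Cochran-Mantel-Haenszel family includes a general-association statistic that ignores order, so widening the parenthesis alone might not produce a trend test for either kind of event.

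A much larger loss can be made to appear by setting the dose rates at 10/20/40% and BCG at 20%, and comparing 73% for the trend with 25% for Fisher, top dose against BCG. Those tests answer different questions, so the difference is not the cost of omitting a trend test.

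The narrowing may be deliberate: Section 10.1 treats solicited injection-site reactions as causally related to product and makes no such rule for systemic events. That could justify the choice, but the plan does not give it as a reason, and it leaves the mismatch with Section 10.2.2. The later analysis plan may add the test, so it cannot be said that systemic events will never be tested for trend.

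The points about cohort drift and multiple tests stand, and they shape the fix.

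**Conclusion.** The point holds as a modest inconsistency with a cheap remedy. The dose-effect test in Section 12.4.4.1 is narrower than the definition in Section 10.2.2, and these documents plan no ordered-dose test for the seven systemic primary events. If all three doses are given and rates rise with dose as assumed, the cost is about 11-13 points of power against an unordered chi-square. No version is well powered.

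The result rests on assumed event rates, equally spaced scores, a two-sided 5% level and no drift between cohorts. In the fallback design the gain is close to nil. A reader might infer that a dose-related rise would therefore be missed when the Phase III dose is chosen. The documents do not support that: selection rests on DSMB review of all the safety data, with no significance rule, and all testing is informal (Section 12.1). What would improve is the sensitivity of the description, not a confirmatory conclusion.

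**What to change.** In Section 12.4.4.1, and in the analysis plan still to be finalized:

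1. Change the parenthesis to *(solicited injection-site and solicited systemic adverse events)*. If the restriction to local events is intended, say so and give the reason.
2. State that the test is the 1-df Cochran-Mantel-Haenszel correlation (trend) statistic across the MTBVAC doses, and give the dose scores.
3. Make any solicited systemic adverse event the lead summary. Treat the seven individual events, and Grade 2 or higher, as descriptive.
4. Keep the planned comparisons with BCG.
5. Beside the trend result, show the systemic event rates of the concurrent BCG infants by cohort. With 8 per cohort this is a coarse check, but it helps keep drift from being read as a dose effect.

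The cost is a few sentences and one more table from data already collected, with no extra infants or visits. The downsides are a few more informal p-values and little gain if only two MTBVAC doses are given.

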12.4.4.2 Clinical Laboratory and Vital Sign Parameters

For each clinical laboratory parameter and vital sign parameter pre-specified in the protocol, summary statistics for continuous parameters will be presented by treatment group for all pre-and post-vaccination assessments and for change from pre-vaccination to post-vaccination assessments.

The number and percentage of participants with post-vaccination Grade 3 or higher clinical laboratory values or vital sign values (Appendices B, C and D) will be tabulated at each post-vaccination time point and overall. Clinical laboratory and vital sign abnormalities will also be reported as adverse events as applicable and will be included in the summaries of adverse events

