3.3 Potential Risks and Benefits

3.3.1 Potential Risks

The safety profile of MTBVAC at the highest dose to be tested (2.5 x 10⁶ CFU) is not yet known in infants. Therefore, vaccination of newborns will be staggered to allow gradual evaluation of safety and reactogenicity at each escalation of MTBVAC dose. Progression from the 2.5 x10⁵ to the 2.5 x10⁶ CFU dose level, for which safety in infants has not yet been demonstrated, will require that all of the following criteria have been met: (1) no pre-defined pausing rules have been observed at lower MTBVAC dose levels in this trial; (2) favourable review of day 28

safety data of all lower MTBVAC dose groups by the Data Safety Monitoring Board (DSMB); (3) favourable review of safety data from the current pilot Phase 1b infant trial by the DSMB; and (4) favourable review of day 28 safety data for the 2.5 x 10⁶ CFU dose level in QFT negative adults in the parallel adult trial by the DSMB. In the event that any one of these safety criteria are not met, Cohorts 1 and 2 will be expanded so that 33 additional neonates will randomly allocated to receive the 2.5 x 10⁴ CFU dose (n=12), the 2.5 x 10⁵ CFU dose (n=13) or BCG (n=8) by default. If there is a delay in adult data, dose escalation in infants will either be delayed, or Cohorts 1 and 2 be expanded as mentioned above.

MTBVAC Data Safety Monitoring Board Charter has been created as a guidance.

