When an adverse event is judged to be related to an investigational product, is judged to be serious and unexpected, and is in a participant who received active vaccine, it is a SUSAR (suspected unexpected serious adverse reaction) and is subject to expedited reporting.

10.2.4 Procedures to be Followed in the Event of Abnormal Laboratory Test Values or Abnormal Clinical Findings

Results from clinical assessments and laboratory tests obtained on the study must be reviewed by the investigator, and the participant managed in accordance with the clinical trial site policies. The clinical significance of any change in a vital sign or laboratory parameter will be determined by the investigator and may be reported as an adverse event at the discretion of the investigator (using the toxicity tables in Appendix B, C and D to grade severity). Additional laboratory tests may be performed if the investigator deems them to be necessary to fully evaluate an adverse event. In the event that the investigator elects to order non-protocol-specified laboratory tests, the investigator must record the rationale for the tests and a determination of clinical significance of the result in the source documents. The investigator must keep the medical monitor informed of vaccine-related adverse events of clinical significance.

Abnormal results and findings will be discussed as applicable with the participant, and the participant will be referred for follow-up with their healthcare provider if necessary.

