APPENDIX C. TABLE OF TOXICITY REFERENCE RANGES FOR GRADING SAFETY LABORATORY EVENTS

Serum/Plasma Chemistry	Grade 1	Grade 2	Grade 3	Grade 4
Sodium – hyponatremia				
mEq/L or mmol/L:	132 – 134	130 – 131	<130	N/A
Sodium – hypernatremia		147-148		
mEq/L or mmol/L:	145- 146	147-140	>148	N/A
Potassium – hyperkalemia				
mEq/L or mmol/L				N/A
≤ 1 year:	5.3 – 5.4	5.5 – 5.6	>5.6	14// (
1 - 2years:	5.1 – 5.2	5.3 – 5.4	>5.4	
Potassium – hypokalemia	0.5.00	0000	0.4.00	N/A
mEq/L or mmol/L:	3.5 – 3.6	3.3 – 3.4	3.1 – 3.2	
Glucose – hypoglycemia	55.50	50.54	.50	N1/A
mg/dL:	55-59	50-54	<50	N/A
mmol/L:	3.0 – 3.2	2.8 – 2.9	<2.8	
Glucose – hyperglycemia	404 440	444 405	. 405	
Fasting - mg/dL:	101 – 110	111 – 125	>125	NI/A
mmol/L:	5.7 – 6.0	6.1 – 6.8	>6.8	N/A
Random – mg/dL:	110 - 125 6.1 – 6.8	126 - 200	>200	
mmol/L:	0.1 - 0.0	6.9 – 11.0	>11.0	
Blood urea nitrogen (BUN) –				
increased	21 – 24	25 – 28	>28	N/A
mg/dL: mmol/L:	7.5 – 8.9	9.0 – 10.0	>10.0	
Creatinine – increased				
mg/dL:	0.8 – 0.9	1.0 – 1.2	>1.2	N/A
umol/L:	66 - 82	83 – 100	>100	19/7
Calcium – hypocalcemia	00 - 02	00 100	7 100	
mg/dL:	8.0 – 8.4	7.5 – 7.9	<7.5	N/A
mmol/L:	2.00 – 2.10	1.87 – 1.99	<1.87	14// (
Calcium – hypercalcemia				
mg/dL:	11.1-11.3	11.4 – 11.6	>11.6	N/A
mmol/L:	2.78 – 2.84	2.85 – 2.92	>2.92	
Magnesium – hypomagnesemia				
mg/dL:	1.3 – 1.5	1.1 – 1.2	<1.1	N/A
mmol/L:	0.52 - 0.62	0.43 - 0.51	<0.43	
Phosphorus – hypophosphatemia				
mg/dL:	2.3 - 2.5	2.0 - 2.2	<2.0	N/A
mmol/L:	0.73 – 0.80	0.63 - 0.72	<0.63	
Albumin – hypoalbuminemia				
g/dL:	2.5 – 2.7	2.2 - 2.4	<2.2	N/A
g/L:	25 – 27	22 – 24	<22	
Total protein – hypoproteinemia				
g/dL:	4.4 - 4.6	4.1 - 4.3	<4.1	N/A
g/L:	44 – 46	41 – 43	<41	
Alkaline phosphatase (ALP)	1.1 – 2.0 x	2.1 – 3.0 x ULN	3.1 – 10 x ULN	>10 x ULN
- increased	ULN**			
Liver Function Tests (LFT) AST, ALT, GGT – increased	1.1 – 2.5 x ULN	2.6 – 5.0 x ULN	5.1 – 10 x ULN	>10 x ULN
Bilirubin (with any increase in LFT) - increased	1.1 – 1.25 x ULN	1.26 – 1.5 x ULN	1.51 – 1.75 x ULN	>1.75 x ULN
- 1110164364	l OLIN	l OLIN	OLIN	

Serum/Plasma Chemistry	Grade 1	Grade 2	Grade 3	Grade 4
Bilirubin (with normal LFT) - increased	1.1 – 1.5 x ULN	1.6 – 2.0 x ULN	2.1 – 3.0 – x ULN	>3.0 x ULN
Cholesterol – increased mg/dL: mmol/L:	171 - 185 5.1 – 5.5	186 – 199 5.6 – 6.0	>199 >6.0	N/A
Pancreatic enzymes amylase, lipase – increased	1.1 – 1.5 x ULN	1.6 – 2.0 x ULN	2.1 – 5.0 x ULN	>5.0 x ULN

Hematology	Grade 1	Grade 2	Grade 3	Grade 4
Hemoglobin g/dL				

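### Section 12.4.4.2 counts graded laboratory values only from Grade 3, so Day 7 values in Grades 1-2 are counted per infant only if the investigator records them as adverse events

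*Combined protocol and SAP*

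**What the plan says.** Section 12.4.4.2 sets out three displays for laboratory and vital-sign data.

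- **Continuous.** For each parameter, "summary statistics for continuous parameters will be presented by treatment group", at pre- and post-vaccination assessments and as change between them. The statistics are not named.
- **Graded.** Participants with "post-vaccination Grade 3 or higher clinical laboratory values or vital sign values" are tabulated, as number and percentage, at each post-vaccination time point and overall. No count of Grades 0, 1 or 2 is described.
- **Adverse events.** "Clinical laboratory and vital sign abnormalities will also be reported as adverse events as applicable" and enter the adverse-event summaries. Section 12.4.4.1 breaks those down by system organ class and preferred term, "as well as by severity and relationship to study vaccine". Section 10.2.1 maps Grade 1 to mild, Grade 2 to moderate, and Grades 3 and 4 to severe.

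Two sections govern whether a laboratory value becomes an adverse event. Section 10.2.1 includes increases in toxicity grade but qualifies laboratory changes as clinically significant. Section 10.2.4 says that a change in a vital sign or laboratory parameter "may be reported as an adverse event at the discretion of the investigator".

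Section 8.3 and Appendix A schedule one safety blood sample, at Day 7 (AST, ALT, GGT, total bilirubin, creatinine, full blood count with differential, platelets). No laboratory sample is scheduled at screening or Day 0.

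**The concern.** Section 12.2 says the trial is sized for common safety events, major signals and important trends, not rare events. With 25 infants per dose, a table that begins at Grade 3 describes the rare end of the distribution. A dose-related change in laboratory values that stays in Grades 1-2 adds nothing to it, however many infants are affected.

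This matters most at the top dose. Section 3.3.1 states that "The safety profile of MTBVAC at the highest dose to be tested" is not yet known in infants, and Section 12.3.1 bases the choice of Phase III dose on all available safety data. The final report should be able to say how many infants on each dose, and on BCG, had a liver enzyme or blood count outside the Grade 0 range. Under the plan as written, that number depends on which values an investigator judged worth recording.

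**Working it through.** The documents give no laboratory event rate, power or precision figure on this point, so there is no planned number to reproduce. The check sets the sections side by side and adds a small illustration.

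**1. What falls below the cut-off (Appendix C).**

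| Day 7 parameter | Grades 1-2 | Grade 3 starts |
|---|---|---|
| AST, ALT, GGT | 1.1-5.0 x ULN | 5.1 x ULN |
| Eosinophils (cells/mm³) | 850-5,000 | above 5,000 |
| Creatinine (mg/dL) | 0.8-1.2 | above 1.2 |
| Platelets (cells/mm³) | 100,000-140,000 | below 100,000 |

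The uncounted band is wide for liver enzymes and eosinophils and narrow for creatinine and platelets.

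**2. Where a Grade 1-2 value can appear.**

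- Grade 3+ table: no.
- Continuous summary: yes, as part of the group statistics, without a count of infants.
- Adverse-event tables: yes, as mild or moderate, but only if it was judged clinically significant and recorded. By contrast, Section 10.1 requires injection-site findings that meet the toxicity-table criteria to be recorded.

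**3. Change from pre-vaccination.** Post-vaccination samples scheduled: one (Day 7). Pre-vaccination samples scheduled: none. The planned change therefore has no starting value for any laboratory parameter. Vital signs do have a Day 0 value, so their change can be calculated.

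**4. Illustration (assumed counts).** Group sizes: 25 per MTBVAC dose and 3 x 8 = 24 BCG pooled over cohorts; 3 x (25 + 8) = 99, as stated. Suppose 10 of 25 infants on a dose and 2 of 24 on BCG have a Grade 1-2 liver enzyme, and none has Grade 3 or higher.

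- Planned graded table: 0/25 against 0/24.
- Exact two-sided 95% upper limit for the Grade 3+ rate at 0/25: 1 - 0.025^(1/25) = 13.7%. This says nothing about Grades 1-2.
- All-grade table: 10/25 = 40.0% against 2/24 = 8.3%, a difference of 31.7 percentage points.
- Newcombe 95% interval, from Wilson limits 23.4-59.3% and 2.3-25.8%: lower = 31.7 - √[(40.0 - 23.4)² + (25.8 - 8.3)²] = 7.5; upper = 31.7 + √[(59.3 - 40.0)² + (8.3 - 2.3)²] = 51.8 points.

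The planned graded table would be the same whether the Grade 1-2 counts were 10 and 2 or 0 and 0.

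**5. When a per-infant count adds most.** If 6 of 25 infants rise sharply and 19 do not, the group median (the 13th ordered value) still lies among the 19 unaffected infants. The mean would move, but it would not show that six infants were responsible.

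**The case against.** **A Grade 1-2 rise does not vanish from the report.** A reader might infer that it would show as zero events. The documents do not support that. The zero belongs to one table out of three: group summaries have no grade limit, and recorded adverse events of any grade are counted by severity. This stands in full.

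**For a uniform shift, the continuous data are more sensitive than a grade count.** Assume log-normal enzyme values with 10% of BCG infants above 1.1 x ULN, and compare 25 with 24 infants. With log-SD 0.5, a t-test on log values has 79% power for a 1.5-fold rise and 99.7% for a 2-fold rise; Fisher's test on Grade 1 or higher has 38% and 91%. None of these inputs comes from the documents, and Section 12.1 rules out formal testing, so power is no argument for the change. The case for it is descriptive.

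**The DSMB would not be misled.** Section 10.7 lets it choose to review laboratory and vital-sign data and unblind safety information as needed. Nothing confines it to the Grade 3+ table, so an inference that it would see no signal is unsupported.

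**Vital signs are better covered.** Fever is a solicited event, so lower-grade fever is counted, and change from Day 0 can be calculated.

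**Section 12.4 is an outline.** A detailed SAP is to be finalised before database lock. No separate SAP text is among the documents, so further grade tables cannot be ruled out. The cut-off in the current text is nevertheless explicit.

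What remains is that no systematic per-infant count exists below Grade 3 for laboratory values.

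**Conclusion.** The point holds as a gap in the description of laboratory safety. The only systematic graded count starts at Grade 3; below it, counting infants depends on investigator judgement. With a single scheduled draw at Day 7 and no pre-vaccination sample, the comparison with BCG rests on post-vaccination values, and a count by grade is a natural way to show them.

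The gap is largest for liver enzymes (1.1-5.0 x ULN) and eosinophils (850-5,000), and smaller for analytes with narrow lower grades. How many infants would fall in it cannot be derived from the documents; the counts of 10 and 2 are assumed. The top dose is part of the case only if Cohort 3 meets the escalation criteria.

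This does not invalidate the safety analysis. It is an inexpensive improvement to a primary objective, the safety comparison with BCG, and worth settling before the SAP is finalised.

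**What to change.** In Section 12.4.4.2 and the SAP:

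1. For each laboratory parameter, tabulate the worst post-vaccination grade (0, 1, 2, 3, 4) by MTBVAC dose and BCG. Derive grades from the laboratory data, whether or not an adverse event was reported.
2. Keep the Grade 3+ line.
3. For the Day 7 analytes, add the difference from BCG in the proportion with Grade 1 or higher, with a 95% CI, labelled descriptive. State whether BCG means the pooled 24 infants or the 8 in the same cohort.
4. State that change from pre-vaccination applies to vital signs only, because no pre-vaccination laboratory sample is scheduled.
5. State how total bilirubin is graded for this table, since Appendices C and D both grade it.

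A vital-sign table of grade shift from Day 0 is optional.

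The cost is some extra table rows and programming; no new samples, visits or infants are needed. Some Grade 1 values of little clinical weight will be displayed, and the BCG column puts them in context.
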